2. SYNOPSIS

Name of Sponsor/Company: BioCryst Pharmaceuticals Inc.

Name of Investigational Product: BCX9930

Name of Active Ingredient: [REDACTED]

Title of Study: A Phase 2, Open-Label Study to Evaluate the Long-term Safety of Oral BCX9930 in Subjects with Paroxysmal Nocturnal Hemoglobinuria (PNH)

Study centers: Centers that have participated in a previous BCX9930 PNH study

Co-ordinating Investigator: [REDACTED]

Phase of Development: 2

Primary Objective:
 
 To assess long-term safety and tolerability data in eligible subjects with paroxysmal nocturnal hemoglobinuria (PNH) who previously received BCX9930 in a BioCryst-sponsored study and derived benefit from BCX9930 treatment. 
Secondary Objectives:
 
 To assess the continued effectiveness of BCX9930 in treatment of PNH during long-term administration. To evaluate patient-reported outcomes (PRO) of long-term BCX9930 treatment. To collect pharmacokinetic (PK), pharmacodynamic (PD), and complement biomarker data in subjects with PNH for incorporation into meta-study models of population PK and PK/PD. To characterize the effects of BCX9930 in subjects with PNH by clinical measurements and PD and complement biomarkers. To evaluate biomarkers of complement activation during episodes of breakthrough hemolysis (BTH). 
Primary Endpoint:
 
 Measurement of safety and tolerability by subject incidence of graded treatment-emergent adverse events (TEAEs), laboratory abnormalities, changes to vital signs, electrocardiogram (ECG) results, and physical examination findings.

Secondary Endpoints:

- Clinical PNH symptom assessments including fatigue, dyspnea, chest pain/discomfort, difficulty swallowing (esophageal pain), abdominal pain, headache, erectile dysfunction, hemoglobinuria, jaundice, incidence of BTH, and incidence of thromboembolic events.
- Clinical measurements of PNH (lactate dehydrogenase [LDH], hemoglobin, haptoglobin, reticulocytes, transfusion requirements).
- PRO endpoints will include scores from the Quality of Life Questionnaire for Patients with Aplastic Anemia/PNH (QLQ-AA/PNH), Functional Assessment of Chronic Illness Therapy (FACIT) fatigue scale, and Treatment Satisfaction Questionnaire for Medication (TSQM).
- Concentration of BCX9930 in plasma at steady state in subjects with PNH.

Pharmacodynamic (PD) Endpoint:

- PD and complement biomarker measurements will include PNH red blood cell (RBC) and white blood cell (WBC) clone size, plasma Factor Bb levels and alternative complement pathway (AP) activity (as assessed via AP Weislab).
- ██
- ██
- ██

Study Design:

This is an open-label phase 2 study designed to evaluate the long-term safety of daily oral treatment with BCX9930 in subjects who have participated in a previous BCX9930 trial for PNH and showed a benefit of treatment as determined by the Investigator. The study allows continued access to BCX9930 for enrolled subjects.

Methodology:

Subjects who meet all of the inclusion and none of the exclusion criteria will be enrolled into the study. Study visits will occur at Screening, Baseline/Day 1, Week 4, then every 4 weeks up to Week 96. Once subjects have reached Week 96, subsequent study visits will occur every 8 weeks up to Week 144. Additional visits will be required in the case of rising serum creatinine.

Subjects will receive up to 144 weeks of daily BCX9930.

- For subjects directly rolling over from another BCX9930 study without treatment interruption, no screening visit is required. The final on-study visit assessments in the prior BCX9930 study will serve as the baseline assessments for this study; however, additional relevant baseline assessments for this study may be performed at the final on-treatment visit for the prior study as needed to satisfy enrollment criteria. Enrollment without treatment interruption into the current study will obviate the requirement for a follow-up visit in the previous BCX9930 study.
- Subjects with an interruption of treatment of 1 to 30 days duration will be required to complete a full baseline visit, but no screening visit.
- Subjects with an interruption of treatment of 31 days or greater will be required to complete a full screening visit and then baseline visit.

Prior to this amendment, the protocol-specified dosing regimen was 500 mg BCX9930 twice daily (BID). Under this amendment, subjects will receive 400 mg BCX9930 BID.

Safety and tolerability will be evaluated through assessments of TEAEs, laboratory analyses (clinical chemistry, hematology, coagulation and urinalysis), vital signs, ECGs, and physical examination findings. Safety events of special interest, including infections, will be followed.

Clinical effectiveness will be assessed at each visit, including assessment of PNH-associated clinical symptoms (eg, fatigue, dyspnea, chest pain/discomfort, difficulty swallowing (esophageal pain), abdominal pain, headache, erectile dysfunction, hemoglobinuria, jaundice), LDH, hemoglobin and haptoglobin levels, reticulocyte counts, number of blood transfusions, BTH and thromboembolic events.

PK and PD samples will be collected at each study visit from baseline onwards and at the time of any suspected breakthrough events. PD and complement biomarkers will include PNH RBC and WBC clone size, and plasma Factor Bb and AP activity. Additional exploratory PD and complement biomarkers may be included, if suitable tests are available.

Sample Size Justification:

No sample size calculations were conducted for this open-label, long-term safety study. Approximately 200 subjects with PNH may be enrolled in this study, to allow continued access to BCX9930 following clinical benefit in a prior BCX9930 trial.

Number of Subjects (planned):

Approximately 200 subjects based upon the anticipated clinical programs for BCX9930.

Inclusion Criteria:

1. Able to provide written informed consent.
2. Male or non-pregnant, non-lactating female subjects.
3. Subjects who have successfully participated in a previous BCX9930 study of PNH and who experienced a clinical benefit, as confirmed by the Investigator. Successful participation is defined as completion of planned duration of dosing with BCX9930 in the prior study, not inclusive of any extension period.
4. Female participants must meet at least 1 of the following contraception requirements:
 - a. Be a woman of childbearing potential who agrees to use a highly effective contraceptive method throughout the study and for a duration of 30 days after the last dose of study drug.
 - b. Alternatively, true abstinence is acceptable for women of childbearing potential when it is in line with the subject's preferred and usual lifestyle.
 - c. Be a woman of nonchildbearing potential.
5. Male participants must meet the following contraception requirements:
 - a. Subjects with female partners of childbearing potential must agree to utilize a highly effective contraceptive method.

- b. Alternatively, true abstinence is acceptable when it is in line with the subject's preferred and usual lifestyle.
6. In the opinion of the Investigator, the subject is expected to adequately comply with all required study procedures and restrictions for the duration of the study.

Exclusion Criteria:

1. Any clinically significant medical or psychiatric condition that, in the opinion of the Investigator or Sponsor, would interfere with the subject's ability to participate in the study or participation would increase the risk for that subject.
2. Any clinically significant history of angina, known coronary artery disease, myocardial infarction, syncope, clinically significant cardiac arrhythmias, left ventricular hypertrophy, cardiomyopathy, aortic stenosis, or any other cardiovascular abnormality.
3. Chronic systemic corticosteroid use. Note: Topical, inhaled, ocular, or nasal sprays containing corticosteroids are allowed.
4. Investigational drug exposure, other than BCX9930, within 30 days of the baseline visit, or 5.5 half-lives of the investigational drug (whichever is longer).
5. For subjects requiring a screening visit:
 - a. Clinically significant abnormal ECG at the screening visit. This includes, but is not limited to, a QT interval corrected using Fridericia's method (QTcF) > 450 msec in males and > 470 msec in females, or ventricular and/or atrial premature contractions that are more frequent than occasional, and/or as couplets or higher in grouping.
 - b. Alanine aminotransferase (ALT) or aspartate aminotransferase (AST) > 3 × upper limit of normal (ULN) (Exception: Subjects may be enrolled with ALT or AST > 3 × ULN if explained by hemolysis. In these cases, ALT and AST must be < 5 × ULN.)
 - c. Total serum bilirubin > 2 × upper limit of normal (ULN) (Exceptions: Subject may be enrolled with total serum bilirubin > 2 × ULN if the elevated bilirubin is explained by hemolysis or in the case of Gilbert's syndrome. In the case of hemolysis, total serum bilirubin must be < 5 × ULN and in the case of Gilbert's Syndrome, total bilirubin must be < 7 × ULN).
6. Daily use of medications listed in the currently applicable prohibited medications list.
7. Pregnant, planning to become pregnant, or having been pregnant within 90 days of baseline, or lactating.

Investigational Product, Dosage and Mode of Administration:

BCX9930 tablets for oral administration. Under this amendment, subjects will take 400 mg BCX9930 BID orally. Dosage forms may include 100, 200, and/or 250 mg tablets to allow for dose adjustments if needed for the safety management of the subject. Clinical effectiveness and safety will be monitored.

Duration of Treatment:

Subjects will be eligible to receive study drug (BCX9930) for 144 weeks, or until drug is available by another mechanism (eg, expanded or market access) or until the Sponsor discontinues development of the product for PNH; whichever comes first.

Reference Therapy, Dosage and Mode of Administration:

N/A

Criteria for Evaluation:Safety:

Safety will be evaluated by TEAEs, laboratory analyses (clinical chemistry, hematology, coagulation, urinalysis with microscopy), vital signs, ECGs, and physical examination findings. An independent data monitoring committee (DMC) will review safety data in accordance with a separate DMC Charter.

Effectiveness:

Clinical measurements of PNH include LDH, hemoglobin and haptoglobin levels, reticulocyte counts, PNH symptoms (eg, fatigue, dyspnea, chest pain/discomfort, difficulty swallowing (esophageal pain), abdominal pain, headache, erectile dysfunction, hemoglobinuria, jaundice), number of blood transfusions, BTH, and thromboembolic events will be used to assess ongoing effectiveness.

Patient Reported Outcomes:

Questionnaires will be used to evaluate quality of life (QLQ-AA/PNH), effectiveness of therapy (FACIT fatigue scale) and treatment satisfaction (TSQM).

Pharmacokinetics:

Plasma samples for determination of BCX9930/metabolite concentrations will be collected at each study visit. Spot urine samples for determination of BCX9930/metabolite concentrations will be collected at each study visit. The resulting PK data will be incorporated into meta-study population PK and PK/PD analyses. Metabolites of BCX9930 will be analyzed as appropriate.

Pharmacodynamics and Complement Biomarkers:

Ex-vivo PD and complement biomarker effects of BCX9930 will be assessed using exploratory assays. Samples collected for PD and complement biomarker analysis may be run in more than one assay to elucidate the PD effects of BCX9930. These include:

- Plasma Factor Bb
- PNH RBC and WBC clone size
- AP activity

The ongoing assessment of the activity of BCX9930 and/or availability of a suitable assay may change the required PD assessments over time. [REDACTED]

Statistical Methods:*Analysis of Safety*

Safety endpoints will be summarized and will include the proportion of subjects: with TEAEs; who discontinue due to a TEAE; who receive a reduced dose due to tolerability issues; who experience a treatment-emergent serious adverse event (SAE); who experience a Grade 3 or 4 TEAE; who experience a treatment-emergent, treatment-related adverse event (AE) consistent with a drug rash (eg, rash, maculo-papular exanthem, papular rash); and who experience Grade 3 or 4 laboratory abnormalities.

AEs will be mapped to a Medical Dictionary for Regulatory Activities (MedDRA) preferred term and system organ classification. The occurrence of TEAEs will be summarized using MedDRA preferred terms, system organ classifications, and severity. In addition to severity, AEs and SAEs will also be summarized based on Investigator assessment of relationship to study drug.

Time to dose reduction, time to discontinuation due to a TEAE, and time to development of drug-related rash will be estimated using the Kaplan-Meier method. For those with a drug-related rash, clinical and laboratory findings will be summarized as will the proportion of subjects who successfully continue therapy following onset of rash.

Descriptive statistics for vital signs, weight, and clinical laboratory results will be presented by study visit. Laboratory abnormalities will be graded according to the Division of Microbiology and Infectious Diseases (DMID) Adult Toxicity Table. The number and percentage of subjects experiencing treatment-emergent graded toxicities will be summarized.

Laboratory toxicity shifts from baseline to the worst post-baseline value as well as the last visit will be summarized. The number and percentage of subjects having elevations in ALT, AST, or bilirubin abnormalities in relation to fold above ULN will be summarized according to the United States Food and Drug Administration's Premarketing Clinical Evaluation on Drug-Induced Liver Injury Guidance for Industry.

Clinically significant abnormal ECG findings will be summarized by study visit. Changes from baseline in ECG parameters will also be summarized by study visit. The number and proportion of subjects with clinically important absolute and change-from-baseline thresholds in QTcF will be summarized.

Analysis of Clinical Measurements of PNH

Clinical measurements of PNH (eg, LDH, hemoglobin, absolute reticulocyte count, haptoglobin levels, number of blood transfusions, incidence of BTH, incidence of thromboses and major thromboses, AST, total bilirubin, and direct bilirubin) will be summarized by summary statistics, including change from baseline, by treatment group and study visit. Categorical measurements will be summarized with frequencies and percentages by treatment group and study visit.

Analysis of Effectiveness and Patient Reported Outcomes

Effectiveness and patient-reported outcomes (PROs) will be monitored with disease-specific clinical assessments, laboratory assessments, and questionnaires. Responses for subjects with PNH will be categorized using published draft criteria (Risitano, Marotta, et al. 2019) into complete response, major response, good response, partial response, minor response, and no response, modified for study duration and visit schedule.

PROs will include FACIT fatigue scale, TSQM, and QLQ-AA/PNH questionnaires.

Analysis of Pharmacokinetic Data

Plasma and urine concentrations of BCX9930 and metabolites (as applicable) will be summarized by dose regimen and study visit. The resulting PK data will be pooled in a meta-analysis of population PK.

Analysis of Pharmacodynamic Data

Descriptive statistics, including change from baseline, will be provided by study visit and dose regimen. The resulting PD data will be explored using model-based techniques pooled in meta-analyses of PK/PD, as applicable.

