- ^c Visits should be every 4 weeks until a subject has completed a total of 96 weeks on treatment with BCX9930 (ie, weeks in this study plus weeks in the previous study).
- ^d Subjects will sCr elevations will be required to complete additional assessments to monitor for potential renal toxicity at the investigational site, at a remote laboratory more convenient for the subject, or via a home health service (where permitted and available) as indicated in Section 11.3.4.1 and Section 13.9.5.3.
- ^e Monitoring for the onset of hemolysis will be conducted after each subject stops BCX9930 treatment. Depending on the results, additional hemolysis testing may continue.
- ^f Informed consent will be signed at the screening visit for subjects requiring a screening visit and will be signed for all other subjects at the baseline visit or final on treatment visit in the prior study (which serves as the subject's baseline visit in this study).
- ^g Medical and medication history should include vaccination history status, assess risk of exposure, and arrange for any appropriate vaccinations to be administered based on local recommendations as well as individual subject considerations.
- ^h BMI calculation and height at screening; weight is to be recorded at each in-clinic visit.
- ⁱ Full physical examinations will be performed at screening and baseline; symptom-directed physical examinations will be performed at all post-baseline visits.
- ^j All ECGs during the study will be single assessments. ECGs will be conducted every 12 weeks up to Week 96 (ie, Weeks 12, 24, 36, 48, 60, 72, 84, and 96) and every 24 weeks thereafter (ie, Weeks 120 and 144) during the treatment period.
- ^k For women of childbearing potential, a serum pregnancy test will be administered at screening; urine pregnancy tests will be assessed at all subsequent visits. Starting at Week 100, women of childbearing potential will start performing urine pregnancy tests at home every 4 weeks (i.e., in between clinic visits). The results will be recorded by the site. If the urine pregnancy test is positive, the subject should contact the site immediately.

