14. STATISTICS

14.1. Sample Size Considerations

No sample size calculations were conducted for this open-label, long-term safety study. Approximately 200 subjects may be enrolled in this study, to allow continued access to BCX9930 following a subject's participation in a prior BCX9930 study.

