#### 5.7.12. Windowing and Multiple Lab Values

Unscheduled and early termination visits will be assigned to an analysis window according to the study day of the actual visit date using visit windows described in Table 3 below:

Visit	Relative Target Day	Analysis Visit Window
Screening (optional)	-35 to -1	Prior to Day 1
Day 1 (Baseline)	1	1
Week 4	29	2 to 43
Weeks 8 to 92	Week * 7 +1	Target Day -13 to Target Day +14
Week 96	673	660 to 701
Week 104 to 136	Week * 7 +1	Target Day -27 to Target Day +28
Week 144	1009	982 and later

Table 3:Visit Windows

For subjects with multiple lab values on the same day, special rules will be used to choose values eligible for display on tables and figures. For South African sites: on days with multiple test results, results from the local lab will be used. For other sites: on days with multiple test results, results from the central lab will be used. If there are still multiple records on the same date, then the median of available records on that date will be used; for these created median records, if applicable, the most frequent toxicity grade of the records used to calculate the median will be used.

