## 8.1.4.4. Disease Severity

Disease severity will be summarized by treatment category, visit, and by PNH symptom category (fatigue, dyspnea, chest pain/discomfort, difficulty swallowing, abdominal pain, headache, erectile dysfunction, hemoglobinuria, jaundice). The number of subjects with a symptom at each visit will be presented, along with a summary of the number of days with symptoms and the severity.

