#### **10.1.2.** Clinical Measurements of PNH

Continuous clinical measurements of PNH (LDH, hemoglobin, haptoglobin levels, absolute reticulocyte count, AST, total bilirubin, and direct bilirubin) will be summarized by summary statistics including change from baseline and percent change from baseline, by treatment category and study visit. Note that LDH, hemoglobin, haptoglobin, and absolute reticulocyte count that occur within a transfusion-impacted period will not be included in summaries but will be presented in respective listings. Categorical clinical measurements of PNH (number of blood transfusions, incidence of major thromboses) will be summarized with counts and percentages by treatment category (see Section 12.3 for a list of thrombosis events). Incidence of breakthrough hemolysis will be analyzed by the sponsor.

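### Transfusions, BTH and thromboses are to be shown by study visit in the protocol and SAP synopsis but without any time axis in SAP 10.1.2; neither works when visit spacing doubles, and equal intervals with person-time should replace both

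*Protocol*

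**What the plan says.** **Display rule.** The protocol synopsis and Protocol 14.3.6 list transfusions, BTH and thromboses together with LDH and hemoglobin as clinical measurements of PNH, to be summarized by treatment group and visit. For the categorical ones: "Categorical measurements will be summarized with frequencies and percentages by treatment group and study visit". The SAP synopsis carries the same text. Protocol 14.3.6 then adds, for BTH alone, its frequency and the time to first episode by treatment group, with no visit dimension.

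**SAP body.** SAP 10.1.2 keeps study visit for the continuous measures. Transfusions and major thromboses "will be summarized with counts and percentages by treatment category (see Section 12.3 for a list of thrombosis events"; visit is not mentioned. BTH incidence is left to the sponsor, and SAP Table 7 lists no table or figure for it. SAP 8.1.4.4 summarizes disease severity by visit, "along with a summary of the number of days with symptoms and the severity".

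**Schedule.** After Day 1 the protocol synopsis sets four-weekly visits through Week 96. The spacing then doubles: "Once subjects have reached Week 96, subsequent study visits will occur every 8 weeks up to Week 144". A footnote to the protocol's schedule of assessments ties the switch to total treatment, prior study included: "Visits should be every 4 weeks until a subject has completed a total of 96 weeks on treatment with BCX9930". Protocol 11.3.4 and the SAP schedule repeat this.

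**Scaling.** Neither document gives a rate per unit time, or any other adjustment for interval length, for these measures.

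**The concern.** LDH and hemoglobin are point measurements, so a by-visit table suits them whatever the spacing. Transfusions, BTH episodes and thromboses are different. What is recorded at a visit is what has happened since the last one, so the count depends on how long ago that was. One display rule is applied to both kinds of measure.

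A secondary objective is continued effectiveness during long-term administration, and the synopsis names transfusions, BTH and thromboembolic events among the measures used to judge it. A by-visit table that steps up when visits become sparser could be read as loss of control late in treatment. Conversely, a true halving of the event rate at the switch would look flat, because half the rate over 56 days gives the same expected count as the full rate over 28.

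The alternative in SAP 10.1.2 avoids that distortion only by pooling over the whole study. Treatment may stop before Week 144 for several reasons, so follow-up will be unequal. A pooled count with no person-time shows neither a rate nor a trend.

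**Working it through.** **Figure to reproduce.** There is none: "No sample size calculations were conducted for this open-label, long-term safety study", and no event rate is given. The rates below are assumptions, spanning 0.1 to 12 events per subject-year.

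**Schedule.** Target day = week × 7 + 1 gives Day 673 for Week 96 and Day 1009 for Week 144, as Protocol 11.3.4 states. The nominal interval is 4 × 7 = 28 days before the switch and 8 × 7 = 56 days after it. SAP Table 3 has the same contrast: 13 + 14 + 1 = 28 days for Weeks 8 to 92, and "Target Day -27 to Target Day +28", which is 27 + 28 + 1 = 56 days, for Weeks 104 to 136.

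**Model.** Constant-rate Poisson process, events attributed to the interval since the previous visit.
- Mean count per visit = rate × days / 365.25. The ratio after to before is 56/28 = 2.00 at any rate.
- Percentage with at least one event = 1 − exp(−rate × days / 365.25).

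| Assumed rate per year | 28 days | 56 days | Ratio |
|---|---|---|---|
| 0.1 | 0.8% | 1.5% | 1.99 |
| 0.5 | 3.8% | 7.4% | 1.96 |
| 1 | 7.4% | 14.2% | 1.93 |
| 2 | 14.2% | 26.4% | 1.86 |
| 6 | 36.9% | 60.1% | 1.63 |
| 12 | 60.1% | 84.1% | 1.40 |

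The ratio is nearest 2 for rare events and falls for frequent ones, where most subjects already have an event within 28 days.

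**Mixed intervals.** If prior-study weeks count, a nominal visit can contain some subjects with 28 days behind them and some with 56. With a fraction f on the longer interval, the mean count is rate × 28 × (1 + f) / 365.25. At f = 0.5 it is 1.5 times the 28-day mean. The table would then follow the mix of schedules as well as the disease.

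**After the change.** At 1 event per year the 56-day mean is 0.153, or 0.153 / 2 = 0.077 per 28 days, equal to the mean before the switch. A 24-week interval is 168 days, made of six 28-day or three 56-day intervals. It gives a mean of 168/365.25 = 0.460 and 36.9% with at least one event on either side of Week 96. Week 96 falls on a boundary (96/24 = 4), and 144/24 = 6 intervals cover the study.

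**The case against.** The strongest reply is that the SAP is the operative plan. Protocol 14.3 hands methods and time points to it, and SAP 10.1.2 drops study visit for transfusions and major thromboses while keeping it for continuous measures in the same paragraph. Durability of response is defined by hemoglobin (SAP 8.1.1). Transfusions also feed the hematological response categories at equal 24-week steps (SAP 8.1.2). The study is descriptive, with estimation put ahead of testing (SAP 3.3).

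Much of this stands, and it rules out several stronger readings that a reader might infer:
- *That the planned tables will show false worsening after Week 96.* This is not established for transfusions and major thromboses, because SAP 10.1.2 as written produces no by-visit table of them.
- *That by-visit display is the only rule for BTH.* Protocol 14.3.6 also asks for frequency and time to first BTH by treatment group. Time to first event does not depend on visit spacing in this way.
- *That days with symptoms must inflate.* With a fixed recall period there would be no step.
- *That Weeks 4 and 96 are inflated too, because their Table 3 windows are 42 days.* Table 3 is introduced to place unscheduled and early termination visits; nothing says events are counted by its windows. Counted since the previous visit, both weeks have 28 days on the nominal schedule.
- *That the step falls sharply at Week 96.* Counting prior-study weeks may move it earlier for some subjects.

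The reply does not settle the matter. The SAP synopsis still says by visit, so the SAP disagrees with itself as well as with the protocol. SAP 10.1.2 has no time axis or person-time. The response categories use transfusions as one input, report no transfusion rate, and leave out BTH and thromboses.

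**Conclusion.** The point holds in conditional form. The protocol and SAP synopsis call for a by-visit display of event-type measures, SAP 10.1.2 does not, and the plan must say which applies. Neither is adequate: the first is distorted by visit spacing and the second ignores time and exposure.

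If the by-visit rule were followed, the mean count would double with no change in disease, and the percentage with at least one event would rise about 1.4 to 2.0 fold. For rare events such as thromboses the ratio is close to 2 but the absolute change is small (0.8% to 1.5% at an assumed 0.1 per year). These figures rest on a constant Poisson rate, on assumed rates, and on counting since the previous visit at nominal spacing. For days with symptoms the conclusion also depends on the unstated recall period.

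The consequence is confined to descriptive secondary displays. It is a worthwhile and cheap correction, not a threat to the primary safety assessment.

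**What to change.** 1. In the protocol synopsis, Protocol 14.3.6, the SAP synopsis and SAP 10.1.2, give one rule for transfusions, BTH and thromboses: summarize them by treatment category per equal 24-week interval (Weeks 0–24 to 120–144, matching the time points of SAP 8.1.2), with the number of subjects and the person-time under observation in each. Keep time to first BTH. Apply the same rule to the BTH analysis left to the sponsor.
2. In SAP 8.1.4.4, state the recall period for days with symptoms. If it is the time since the last visit, report those days as a percentage of days since the previous visit.
3. Keep by-visit tables for point measurements such as LDH and hemoglobin.

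Person-time also handles subjects who change schedule before Week 96 and those who stop early. The cost is some wording and one derived interval variable. The downside is coarser time resolution for the event measures.
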